#### **4.1. Device Labeling**

Directions for use (DFU) will be provided to each Investigator. The study devices and packaging are physically identified and labeled as applicable. The device labeling contains the following information:

- Device description
- Model number
- Serial number / Lot number as applicable
- Device dimension (i.e. Length), as applicable
- Manufacturing location
- Expiration date (“use before date”), as applicable
- Labeled for investigational use

### **5. Objectives**

#### **5.1. Primary Objective**

The primary objective of this study is to evaluate the safety and effectiveness of high-rate spinal cord stimulation (HR-SCS) therapy as compared to commercial rate spinal cord stimulation (CR-SCS) therapy as an aid in the management of chronic intractable pain of the trunk, including unilateral or bilateral pain associated with the following: failed back surgery syndrome, intractable low back pain using the Boston Scientific (BSC) PRECISION Spinal Cord Stimulator System Adapted for High Rate Spinal Cord Stimulation (PRECISION SCS System for HR).

#### **5.2. Secondary Objective**

The secondary objective of this study is to determine the impact of HR-SCS therapy on global patient outcomes as an aid in the management of chronic intractable pain of the trunk and/or limbs, including unilateral or bilateral pain associated with the following: failed back surgery syndrome, intractable low back pain and leg pain using the Boston Scientific (BSC) PRECISION SCS System for HR.

## 6. Endpoints

### 6.1. Primary Endpoint

The primary endpoint is the comparison of low back pain responder rate in the HR-SCS group to that of the CR-SCS group at 3 months post-activation, based on reduction from Baseline in average low back pain intensity with no change from Baseline in average daily opioid intake as assessed by the eDiary.

[REDACTED]

[REDACTED]

[REDACTED]

[REDACTED]

[REDACTED]

[REDACTED]

[REDACTED]

[REDACTED]

### ***6.6. Additional Safety Parameter***

Additional safety parameters include the following:

- Rate of occurrence of all adverse events (AEs) through End of Period 2
- Rate of occurrence of all device or procedure related adverse events (AEs), SAEs including serious adverse device events (SADEs), unanticipated adverse device events (UADEs) through end of study.

## **7. Design**

The study is a multi-center, randomized, controlled, non-inferiority, crossover, adaptive, open label design. In this crossover design, eligible subjects will be randomized in a 1:1 ratio to receive one of the following sequences:

- CR-SCS followed by HR-SCS
- HR-SCS followed by CR-SCS

using the Boston Scientific PRECISION™ SCS System and the Boston Scientific PRECISION SCS System for HR. The study is open label, thus the study participants, investigative site personnel, and the sponsor will not be blinded. All subjects will undergo permanent system implantation. The study design is shown in Figure 7-1.

[REDACTED]

[REDACTED]

Confidential

Protocol Template  
ACCELERATE Study

Page 40 of 177

[figure not shown]

Figure 7-1. ACCELERATE Study Design

### ***7.2. Treatment Assignment***

Eligible subjects will be randomized in a 1:1 ratio to receive one of the following sequences:

- CR-SCS followed by HR-SCS
- HR-SCS followed by CR-SCS

Randomization will be implemented in the Electronic Data Capture (EDC) system using a pre-generated randomization table. Random permuted blocks stratified by site will be employed to ensure approximate balance of treatment allocation.

### ***7.3. Treatment and Control***

The treatment device is the Boston Scientific PRECISION SCS System with high-rate stimulation parameters. The control device is the Boston Scientific PRECISION™ SCS System with commercially approved stimulation parameters. See Section 4 for details regarding HR-SCS and CR-SCS therapies.

### ***7.4. Justification for the Study Design***

The study is a randomized controlled crossover, non-inferiority, adaptive, open label study of spinal cord stimulation using high rate stimulation parameters for the treatment of chronic intractable pain as compared to commercial rate stimulation parameters. The study will evaluate if high rate stimulation parameters are non-inferior to commercially approved stimulation parameters in the reduction of low back pain intensity in the population with chronic pain (See Section 8 for study inclusion and exclusion criteria). Chronic low back pain is historically more difficult to treat than other pain regions (e.g. lower extremity) and thus high rate SCS therapy may allow for expanded treatment options for these patients.

A multi-center design will minimize the impact on treatment outcome that may potentially result from differences in patient selection, regional differences in the patient demographic, and differences in investigator technique and patient management.

A prospective study design will eliminate the bias associated with case selection in a retrospective review and will ensure that identical procedures are followed for data capture and review.

The study design includes two groups (arms) – a treatment group (HR-SCS) and a control group (CR-SCS). The treatment group will receive stimulation using high rate SCS system, while the control group will receive stimulation using a commercially-approved SCS system. The control group will serve as a comparator to the standard-of-care in spinal cord stimulation therapy using currently-approved stimulation rates.

Randomization will be used to minimize selection bias and the impact of demographic variables.

The primary efficacy endpoint will be measured at 90 days post-activation of the SCS system because this represents a duration sufficient for a subject to have their programming parameters optimized as well as to allow for therapy to become stable.

The responder rate, as measured by reduction in baseline low back pain intensity as measured daily using the numerical rating scale during the 15 day period prior to Baseline Visit and 3-months post-activation, was chosen as the primary endpoint as it provides a clinically-relevant metric to assess the pain-relieving impact of the therapy.

The electronic diary will be administered daily under real-life conditions as subjects continue to use their device and medication. The analysis window of 15 consecutive days of electronic diary completion was chosen to adequately capture the normal fluctuations in pain intensity that is typical with chronic pain. Additionally, the numerical rating scale for measuring pain intensity is a validated measure and has been used in other randomized controlled trials to measure the outcomes of SCS.

## **8. Subject Selection**

### ***8.1. Study Population and Eligibility***

Study candidates will be drawn from the population of patients resident in pain management or surgical medical practices. The study eligibility criteria are listed in Sections 8.2 and 8.3.

### ***8.2. Inclusion Criteria***

Subjects who meet all of the following criteria (see Table 9-1) will be considered for inclusion in this clinical investigation, provided no exclusion criterion (see Table 9-2) is met.

**Table 8-1. Inclusion Criteria**

Clinical Inclusion Criteria	IC1. Complaint of persistent or recurrent low back pain, with or without equal or lesser leg pain, for at least 180 days prior to Screening [REDACTED] [REDACTED] [REDACTED]
	IC5. Average low back pain intensity, during the position/activity which routinely causes worst pain, of 5 or greater on a 0-10 numerical rating scale during the 7-day period prior to Screening based on study candidate recall [REDACTED] [REDACTED] [REDACTED]
	IC10. Willing and able to comply with all protocol-required procedures and assessments/evaluations (e.g. willing to comply with opioid prescription lock from the Medication Lock Visit through End of Period 2 and protocol required stimulation parameter locks, complete daily diary) [REDACTED] [REDACTED]
	IC13. 22 years of age or older when written informed consent is obtained
	IC14. Able to independently read and complete all questionnaires and assessments provided in English
	IC15. If female of childbearing potential: not pregnant, as evidenced by a negative pregnancy test at Screening
	IC16. Subject signed a valid, IRB-approved informed consent form (ICF) provided in English

### 8.3. *Exclusion Criteria*

Subjects who meet any one of the following criteria (Table 9-2) will be excluded from this clinical study.

**Table 8-2. Exclusion Criteria**

Clinical Exclusion Criteria	
EC9. Any pain-related diagnosis or medical/psychological condition that, in the clinician's best judgment, might confound reporting of study outcomes (e.g. pelvic pain, anginal pain, chronic migraine)
 
EC12. Current systemic infection, or local infection in close proximity to anticipated surgical field, at Screening
 
EC17. Current condition associated with risk of immunocompromise that might increase risk of infection during study duration

-----------------------------------	--

- EC20. Significant cognitive impairment at Screening that, in the opinion of the Investigator, would reasonably be expected to impair the study candidate's ability to assess pain intensity and/or complete an electronic pain diary
- EC21. Participating (or intends to participate) in another drug or device clinical trial that may influence the data that will be collected for this study
- EC22. Previous spinal cord stimulation trial or is already implanted with an active implantable device(s) (e.g. pacemaker, drug pump, implantable pulse generator)
- EC23. A female who is breastfeeding
- EC24. A female of childbearing potential planning to get pregnant during the course of the study or not using adequate contraception

	EC27. Any injury or medical/psychological condition that might be significantly exacerbated by the implant surgery or the presence of an implantable stimulator or otherwise compromise subject safety
--	--

## 9. Subject Accountability

### 9.1. *Point of Enrollment*

A subject will be considered enrolled in the study at the time that the informed consent form is signed. Subjects who are discontinued prior to randomization are considered “enrolled but not randomized.” All enrolled and randomized subjects will be included in the study analyses.

If device implantation is unsuccessful, the subject will be followed for 2 weeks post implantation attempt to assess for procedure related adverse events. Implant failures will be withdrawn from the study and will be handled as described in Section 10.2.

### 9.2. *Withdrawal*

All subjects enrolled in the clinical study (including those withdrawn from the clinical study or lost to follow-up) shall be accounted for and documented. If a subject withdraws from the clinical investigation, the reason(s) shall be reported. If such withdrawal is due to problems related to investigational device safety or performance, the investigator shall ask for the subject’s permission to follow his/her status/condition outside of the clinical study.

While study withdrawal is discouraged, subjects may withdraw from the study at any time, with or without reason and without prejudice to further treatment. In all cases of withdrawal or discontinuation, the Investigator will make all reasonable efforts to determine the reason for the subject’s withdrawal. Subjects may be discontinued from the study for the various reasons, such as:

- Withdrawal of consent;
- A safety concern defined by the Principal Investigator and/or BSN (e.g., adverse event);
- Study non-compliance;
- Subject did not meet inclusion criteria or met an exclusion criteria after signing informed consent
- Subjects not agreeing to a recommended revision;
- Loss to follow-up;
- Death of the subject.

Withdrawn subjects will be followed per End of Study Action Plan.

### ***9.3. Subject Status and Classification***

Subjects who provide written informed consent but do not meet all of the study eligibility criteria will not be implanted and randomized. These subjects will be deemed as “enrolled but not randomized” and their reason for ineligibility will be documented in the EDC system. Enrolled subjects who are not randomized will not count towards the enrollment cap. Subjects who sign consent, meet all eligibility criteria, and are randomized cannot be replaced.

[REDACTED]

[REDACTED]

### ***9.5. End-of-Study Action Plan***

The End-of-Study Action Plan (ESAP) defines the actions to be taken when a subject reaches the end of their study participation. At the time of subject withdrawal or during the last study follow-up visit the ESAP will be implemented.

All ESAP decisions made by a subject need to be documented in the subject’s source documents.

Device related medical events/deficiencies should be reported to BSN Patient Care at: **[contact]** for subjects who choose to retain the device after withdrawal or who have completed participation prior to approval of the device. Such complications should not be captured as adverse events in the EDC system.

If the subject is explanted as part of the ESAP, it is recommended that the subject be evaluated by their study doctor for any complications of the explant procedure and followed for 30 calendar days for adverse events related to the explant procedure or longer until the adverse events have either resolved or stabilized, per investigator discretion. Complications of the explant procedure should be captured as adverse events and/or a device deficiency in the EDC system.

[REDACTED]

Confidential

Protocol Template  
ACCELERATE Study

Page 52 of 177

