#### **10.25. *Study Completion***

All subjects permanently implanted with an IPG will be followed through completion of the End of Study visit. In the event that approval is received prior to all enrolled subjects completing the End of Study visit, all study sites will be notified and all enrolled subjects who have not yet completed the End of Study Visit will no longer be followed per protocol. The End of Study Action Plan (see Section 10.5) defines the actions to be taken when the subject reaches the end of their study participation.

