### ***12.2. Study Assessments***

#### ***12.2.1. Adverse Events***

Adverse event evaluation will be conducted to identify adverse events occurring during the study and classify them in regards to seriousness, relationship to the study procedure and/or device, action taken and outcome. Safety events will be reported as specified in Table 20-3.

- Non-serious AEs which are neither device/procedure related will be collected from the time of informed consent through the end of period 2.
- Adverse events which are device/procedure related will be collected from the time of informed consent through 12 months post-Period 1 activation

Page 92 of 177

- SAEs, SADEs, Device Deficiencies and UADEs will be collected from the time of informed consent through 12 months post-Period 1 activation.

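### Device-related events after withdrawal with a retained implant are barred from the EDC by Section 9.5 but fall inside the 12-month collection window of Section 12.2.1; a crude EDC-based rate under Section 6.6 would be understated

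*Combined protocol and SAP*

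**What the plan says.** All references are to the combined protocol and SAP.

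- **Section 9.2 (Withdrawal):** "Withdrawn subjects will be followed per End of Study Action Plan". The listed reasons include safety concerns, non-compliance and "Subjects not agreeing to a recommended revision". If a withdrawal is due to device safety or performance, the investigator asks for "permission to follow his/her status/condition outside of the clinical study".
- **Section 9.5 (End-of-Study Action Plan):** the plan starts at withdrawal or at the last visit. Device-related events and deficiencies go to the sponsor's patient-care line "for subjects who choose to retain the device after withdrawal", and for subjects who completed before device approval. Then: "Such complications should not be captured as adverse events in the EDC system". Explant is treated differently: "Complications of the explant procedure should be captured as adverse events and/or a device deficiency in the EDC system".
- **Section 12.2.1 (Adverse Events):** "Adverse events which are device/procedure related will be collected from the time of informed consent through 12 months post-Period 1 activation". SAEs, SADEs, UADEs and device deficiencies have the same window. Withdrawal is not mentioned.
- **Section 10.25 (Study Completion):** "All subjects permanently implanted with an IPG will be followed through completion of the End of Study visit". The same section refers to the Action Plan for what happens when participation ends.
- **Section 6.6** reports device- or procedure-related events through end of study. **Section 11.6.3** puts everyone who consented in the safety set. **Section 10.21** expressly keeps subjects withdrawn for refusing a lead revision in the safety analysis.

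**The concern.** Take a subject who withdraws at month 4 with the implant in place and has a first device-related event at month 8. Section 12.2.1 would collect that event; Section 9.5 would keep it out of the EDC as an adverse event. The specific rule for retained devices would ordinarily prevail over the general one. The subject still counts in the safety denominator, but the event does not reach the numerator.

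What is at stake is the completeness of a 12-month device safety rate for an implanted investigational system. Some subjects may withdraw because of a device problem, since refusing a recommended revision is a listed reason. The uncounted time may then belong to subjects at more than average risk.

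**Working it through.** **1. Do the rules overlap?** Section 9.5 sets no time limit and is triggered by withdrawal, so it covers withdrawals before month 12. For subjects who complete the study, the bar broadly agrees with Section 12.2.1, because their window closes at about the End of Study visit. The conflict is confined to subjects who withdraw before month 12 and keep the device.

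**2. Does the lost event reach the Section 6.6 rate?** Section 12.1 says subject data are recorded in the EDC. That the rate is computed from EDC adverse events is an inference from this. If it is a crude rate, the denominator is fixed and events can only be removed from the numerator, so the error is downward. Section 6.6 does not say whether the rate is per subject or per event. Per subject, only first events in subjects still event-free at withdrawal are lost. Per event, later ones are lost too.

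**3. How much of the window is uncovered?** Inputs are the visit schedule (Sections 10.12 to 10.19) at nominal days, with no delay before the Period 2 activation visit.

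- Withdrawal at End of Period 1, day 90: 365 − 90 = 275 days left, 275/365 = 75%.
- Withdrawal at End of Period 2, day 90 + 7 + 15 + 90 = 202: 365 − 202 = 163 days left, 163/365 = 45%.

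**4. How large could the loss be?** The readable text gives no event or withdrawal rate, so there is no plan figure to reproduce. The inputs below are assumptions: 12-month first-event risk of 10% in implanted subjects, constant hazard, and a share w of 5% to 15% withdrawing with the device in place, at the same hazard as everyone else.

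- Hazard: h = −ln(0.90)/365 per day.
- Event-free at day t: S(t) = exp(−h·t). S(90) = 0.9744, S(202) = 0.9434, S(365) = 0.90.
- Omitted first events: w × [S(t) − S(365)].
- Low end, w = 5%, day 202: 0.05 × (0.9434 − 0.90) = 0.0022, about 0.2 points.
- High end, w = 15%, day 90: 0.15 × (0.9744 − 0.90) = 0.0112, about 1.1 points.

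The recorded rate is then about 9.8% or 8.9% against a true 10.0%. Under the same assumptions an estimate censored at withdrawal returns 10.0%.

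**5. Sensitivity to the assumed risk.** Let withdrawal times be uniform over the year, still with no raised hazard. With 12-month risk p and λ = −ln(1 − p), the loss is w × [p − (1 − p/λ)].

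- p = 10%, w = 5%: 0.05 × [0.10 − (1 − 0.10/0.1054)] = 0.25 points.
- p = 30%, w = 20%: 0.20 × [0.30 − (1 − 0.30/0.3567)] = 2.8 points.

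The direction is the same throughout; the size follows the assumptions. Over all consented subjects, some never implanted, both the rate and the loss in points are smaller.

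**The case against.** **The estimator and the governing safety text cannot be read.** Section 19, Table 20-3 and redacted text near Section 9.5 may hold a further rule. Through end of study could also mean each subject's own end of participation. Section 9.5 lends that some support, since withdrawal triggers the plan for subjects reaching that end. On that reading these events fall outside the rate by definition. The fixed window in Section 12.2.1 and the all-consented safety set point the other way, but they do not settle it. This stands as a condition on the finding.

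**Section 10.25 is not an unconditional promise.** A reader might infer a flat contradiction between Sections 10.25 and 9.5. Section 10.25 defers to the Action Plan and ends per-protocol follow-up early if approval comes first, so it does not support that. The conflict is with Section 12.2.1.

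**The most worrying subgroup is partly covered.** An event recorded before withdrawal already counts, and a subject who refuses a revision may well have one. Explant complications are captured, and the Section 9.5 bar does not address events related only to the procedure. This reduces the loss without removing it.

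**A raised hazard cannot be quantified.** A reader might triple the hazard after withdrawal and obtain 0.15 × 0.9744 × 0.2119 = 3.1 points. The documents give no basis for the multiplier. The sum also keeps the average event-free share at withdrawal, although device-linked withdrawers would more often have an event on record already.

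**Conclusion.** The conflict between Sections 9.5 and 12.2.1 is real and is not resolved in the readable text. If the Section 6.6 rate is crude and taken from EDC adverse events, it can only be understated. Under the 10% risk and 5% to 15% withdrawal assumed above, with no raised hazard, the loss is about 0.2 to 1.1 points in implanted subjects. It would be larger if withdrawal is linked to device problems, by an amount that cannot be stated.

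A reader might infer that the plan definitely drops these events from the reported rate, or that the comparison of the two stimulation modes is biased. The first is not established, because the estimator and part of the safety text are not readable. Nothing in the documents shows the second. This is a minor point on an additional safety parameter, and the primary endpoint is not affected.

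**What to change.** 1. Reconcile Sections 9.2, 9.5 and 12.2.1, stating what is collected after withdrawal when the device stays in place.
2. Limit the Section 9.5 bar to events later than 12 months after Period 1 activation, and to subjects who refuse or withdraw consent to further data use.
3. For other subjects withdrawn with the device in place, for example for non-compliance or for refusing a revision, extend the permission step already in Section 9.2. Ask at withdrawal whether device-related events reported to the sponsor up to month 12 may be entered in the EDC, and count those events in the Section 6.6 rate.
4. Apply this prospectively, without re-contacting subjects already withdrawn. The synopsis says common information is not repeated in Appendix A, so the wording would also reach sub-study subjects unless the appendix has its own rule.
5. Report the number withdrawn with the device in place. Next to the crude rate, show a cumulative-incidence estimate censored at withdrawal, noting that it may still understate the rate if withdrawal is related to device problems.

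**Cost:** permission wording with IRB review, data entry for reported events, one count and one extra estimate. No visit or procedure is added. The reported rate may be slightly higher. Phone reports are less complete than visit data, so the change recovers only part of the loss.
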